Cancer surgeries	Specified in 'cancer-related surgery' of section 8.3.2
Benign surgeries	R4123-R4129, R4421, R4430, R3975
Cancer-related event (active cancer)	C00-C97 (excluding non-melanoma skin cancer, C44) with V code (V011, V027, V193, V194)
Kidney function change	
Chronic kidney disease	N18, N19
Acute kidney injury	N17
Liver function change	
Liver disease	B15-B19, K70-K77
Abnormal liver function	R94.5, R74.0

- **Phase II of the study**

- Major bleeding will be defined using primary or secondary diagnosis codes according to the ICD-10 diagnostic codes shown in below table and classified by site (intracranial, gastrointestinal [GI], all others).

Major bleeding	ICD-10 diagnosis code	Diagnostic definition
Intracranial hemorrhage	I60, I61, I62, I690, I691, I692, S064, S065, S066, S068	Diagnosis code + admission code + brain CT or MRI code

		* Brain CT or MRI: CT: HA441, HA451, HA461, HA471, HA851 MRI: HE101, HE102, HE135, HE201, HE202, HE235, HE301, HE302, HE401, HE402, HE501, HE502, HE535
GI bleeding	I850, I983, K2211, K226, K228, K250, K252, K254, K256, K260, K262, K264, K266, K270, K272, K274, K276, K280, K282, K284, K286, K290, K3181, K5521, K625, K920, K921, K922	Diagnosis code + admission code
Other bleeding	D62, H448, H3572, H356, H313, H210, H113, H052, H470, H431, I312, N020-N029, N421, N831, N857, N920, N923, N930, N938, N939, M250, R233, R040, R041, R042, R048, R049, T792, T810, N950, R310, R311, R318, R58, T455, Y442, D683	Diagnosis code + admission code

- The earliest date of diagnosis of the major bleeding event after the index date will be defined as the outcome occurrence date.
- Patients will be followed up from the index date to the occurrence of an outcome, treatment discontinuation (30-day grace period), switch to another anticoagulants, in-hospital death, or end of the study period (31 Dec 2019) whichever comes first.

Potential Confounder(s)

- Sociodemographic characteristics such as age, sex, and index year will be assessed at the index date.
- CCI [2] and HAS-BLED [3] scores will be measured within the 6-month period prior to the index date.

List of CCI	Score	ICD-10 codes
Cerebrovascular disease	1	G45, G46, H34, I60-I69
Congestive heart failure	1	I09.9, I11.0, I13.0, I13.2, I25.5, I42.0, I42.5-I42.9, I43, I50, P29.0
Chronic pulmonary disease	1	I27.8, I27.9, J40-J47, J60-J67, J68.4, J70.1, J70.3

Dementia	1	F00–F03, F05.1, G30, G31.1

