Diabetes without chronic complication	1	E10.0, E10.1, E10.6, E10.8, E10.9, E11.0, E11.1, E11.6, E11.8, E11.9, E12.0, E12.1, E12.6, E12.8, E12.9, E13.0, E13.1, E13.6, E13.8, E13.9, E14.0, E14.1, E14.6, E14.8, E14.9
Mild liver disease	1	B18, K70.0-K70.3, K70.9, K71.3-K71.5, K71.7, K73, K74, K76.0, K76.2-K76.4, K76.8, K76.9, Z94.4
Myocardial infarction	1	I21, I22, I25.2
Peripheral vascular disease	1	I70, I71, I73.1, I73.8, I73.9, I77.1, I79.0, I79.2, K55.1, K55.8, K55.9, Z95.8, Z95.9
Peptic ulcer disease	1	K25-K28
Rheumatologic disease	1	M05, M06, M32–M34, M31.5, M35.1, M35.3, M36.0
Diabetes with chronic complication	2	E10.2–E10.5, E10.7, E11.2–E11.5, E11.7, E12.2–E12.5, E12.7, E13.2–E13.5, E13.7, E14.2–E14.5, E14.7
Hemiplegia or paraplegia	2	G04.1, G11.4, G80.1, G80.2, G81, G82, G83.0-G83.4, G83.9
Any malignancy, including leukemia and lymphoma	2	C00–C26, C30–C34, C37–C41, C43, C45–C58, C60–C76, C81–C85, C88, C90–C97
Renal disease	2	I12.0, I13.1, N03.2-N03.7, N05.2–N05.7, N18, N19, N25.0, Z49.0–Z49.2, Z94.0, Z99.2
Moderate or severe liver disease	3	I85.0, I85.9, I86.4, I98.2, K70.4, K71.1, K72.1, K72.9, K76.5, K76.6, K76.7
AIDS/HIV	6	B20–B22, B24
Metastatic solid tumor	6	C77-C80

List of HAS-BLED	Score	ICD-10 codes

Hypertension	1	I10-I15
Abnormal renal function	1	N18.3, N18.4, N18.5, N19, Z94.0, Z99.2
Abnormal liver function	1	B15-B19, C22, D68.4, I98.2, I98.3, K70-K77, Z94.4
Stroke	1	I63, I69.3, G45.9
Bleeding history	1	Intracranial and GI: I60, I61, I62, I69.0, I69.1, I69.2, S06.4, S06.5, S06.6, S06.8, I85.0, I98.3, K22.11, K22.6, K22.8, K25.0, K25.2, K25.4, K25.6, K26.0, K26.2, K26.4, K26.6, K27.0, K27.2, K27.4, K27.6, K28.0, K28.2, K28.4, K28.6, K29.0, K31.81, K55.21, K62.5, K92.0, K92.1, K92.2 Other sites*: D62, H44.8, H35.72, H35.6, H31.3, H21.0, H11.3, H05.2, H47.0, H43.1, I31.2, N02.0-N02.9, N42.1, N83.1, N85.7, N92.0, N92.3, N93.0, N93.8, N93.9, M25.0, R23.3, R04.0, R04.1, R04.2, R04.8, R04.9, T79.2, T81.0, N95.0, R31.0, R31.1, R31.8, R58, T45.5, Y44.2, D68.3
Labile INR	1	Not applicable
Elderly > 65 years	1	
Drugs or alcohol concomitantly	1	Antiplatelet agents, NSAIDs
	1	Alcoholism: E24.4, F10, G31.2, G62.1, G72.1, I42.6, K29.2, K70, K86.0, O35.4, R78.0, T51.0, X45, X65, Y15, Y90, Y91, Z71.4, Z72.1

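### The intracranial haemorrhage outcome accepts sequela codes I690–I692 without an acute code or a rule that the bleed is new, so an old bleed can be counted as a new event

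*SAP*

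**What the plan says.** The Phase II outcome table in SAP 8.4 lists the intracranial codes as "I60, I61, I62, I690, I691, I692, S064, S065, S066, S068". Protocol section 9.3, Table 2, has the same list. To count, a patient needs "Diagnosis code + admission code + brain CT or MRI code". On position, the SAP says: "Major bleeding will be defined using primary or secondary diagnosis codes according to the ICD-10 diagnostic codes shown in below table". On timing: "The earliest date of diagnosis of the major bleeding event after the index date will be defined as the outcome occurrence date". That event also ends follow-up.

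The same section defines two baseline items for HAS-BLED. The intracranial part of bleeding history is "I60, I61, I62, I69.0, I69.1, I69.2, S06.4, S06.5, S06.6, S06.8". Stroke is "I63, I69.3, G45.9". The window is fixed by "CCI [2] and HAS-BLED [3] scores will be measured within the 6-month period prior to the index date". I69 also appears in the stroke comorbidity, and the Charlson cerebrovascular item runs from I60 to I69.

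In the Phase I table of events preceding treatment change, a new ischaemic stroke is I63 alone, and it must be the first within 6 months. Major bleeding in that table takes over the Phase II definition and is not among the conditions given a newness rule.

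Prior bleeding is not an exclusion criterion (SAP 8.3.2, protocol 9.2.2). One sensitivity analysis removes patients with bleeding history in the 6 months before index (SAP section 10, protocol 9.7).

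**The concern.** I60–I62 and the S06 codes describe a bleed or injury that is happening. I690–I692 describe the lasting consequences of an earlier intracranial bleed. The documents do not define them; this is their meaning in ICD-10. Such a code can be recorded as a secondary diagnosis at any later admission of a survivor. If that admission includes a brain scan, for a fall or a suspected ischaemic stroke for instance, the patient meets the outcome definition without having bled.

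Three things follow. The outcome contains non-events. If these are balanced between groups, the hazard ratio moves towards 1; if drug choice depends on an old bleed that the baseline window does not see, the bias can go either way. And because follow-up stops at the false event, a later true bleed in that patient is lost. The cohort may be rich in such patients, since protocol section 7 names paralysis and long immobilisation among the risk factors for VTE.

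**Working it through.** **1. Code lists side by side**

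| Condition | Baseline history (HAS-BLED) | Event during follow-up |
|---|---|---|
| Ischaemic stroke | I63, I69.3, G45.9 | I63 only, first within 6 months |
| Intracranial bleed | I60–I62, I69.0–I69.2, S06.4–S06.6, S06.8 | the same codes, no newness rule |

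For ischaemic stroke the plan keeps the I69 code for history and leaves it out of the event. For intracranial bleeding it makes no such separation: with the dots removed, the two lists are identical.

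**2. Following the rule for one patient**

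Take a bleed years before index, an admission with brain CT while on treatment, and I69.1 as a secondary diagnosis. The diagnosis code, admission and imaging conditions are all met, and the date is the first such diagnosis after index. The patient counts as an intracranial haemorrhage. No other condition in either document prevents this.

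**3. What the 6-month window does**

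- *I69 code recorded in the 6 months before index.* The patient enters the propensity model through HAS-BLED, the Charlson index and the stroke comorbidity. The sensitivity analysis also removes this patient, provided it uses the HAS-BLED bleeding list; neither document names the list. The main analysis still counts the later I69 code as an event.
- *No such code in that window, first I69 code on treatment.* Nothing captures this patient.

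**4. Size, by illustration only**

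No figure in the plan depends on this point. The inputs in (a) are assumptions: 0.5–2% of patients have an old intracranial bleed, 10–20% of them are admitted and scanned on treatment, and the true on-treatment intracranial risk is 0.2–0.4%. The calculation also assumes an I69 code at every such admission, so for given inputs it is an upper bound.

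(a) Intracranial site. False share = h × s / (h × s + true risk).
- Lowest: 0.005 × 0.10 / (0.0005 + 0.004) = 11%
- Middle: 0.01 × 0.10 / (0.001 + 0.002) = 33%
- Highest: 0.02 × 0.20 / (0.004 + 0.002) = 67%

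(b) All major bleeding. Take the middle case, 0.10% false events, with the event probabilities in SAP section 9.
- Apixaban comparison, 1.19%: 0.10 / (0.10 + 1.19) = 7.8%
- Edoxaban comparison, 8.5%: 0.10 / (0.10 + 8.5) = 1.2%

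The extremes of the assumed inputs run from 0.05 / (0.05 + 8.5) = 0.6% to 0.40 / (0.40 + 1.19) = 25%. The latter needs every input at its least favourable value.

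(c) Hazard ratio and power. As a check on method, Schoenfeld's formula gives events = (1.96 + 0.84)² / [a(1−a)(ln HR)²]. With a = 83/211 and HR 0.75 that is 397.4 events, and 397.4 / 0.0119 = 33,398 patients, against 33,340 in the plan.

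If a share f of warfarin events are old bleeds with hazard ratio 1, the observed HR is (1−f) × HR + f. In the middle case the warfarin risk is 1.19 / (0.607 + 0.393 × 0.75) = 1.32%, so f = 0.10 / (0.10 + 1.32) = 7.0%. The observed HR is then 0.930 × 0.75 + 0.070 = 0.77.

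Power at the projected cohort sizes:

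| Comparison | f = 0 | f = 5% | f = 10% |
|---|---|---|---|
| Apixaban, HR 0.75, false events added to true ones | 92.5% | 91.0% | 89.1% |
| Apixaban, HR 0.75, total events held fixed | 92.5% | 89.4% | 85.4% |
| Dabigatran, HR 0.69, false events added | 87.7% | 85.4% | 82.8% |
| Dabigatran, HR 0.69, total held fixed | 87.7% | 83.5% | 78.5% |

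Only the last cell falls below the planned 80%.

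**The case against.** The admission and imaging requirements already screen out most incidental codes. They narrow the problem but do not show that the bleed is new.

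The protocol takes its bleeding definition from a cited review of research in a Korean national health database, which cannot be seen here, and deleting codes departs from it. That is a cost. It does not turn a past-event code into an incident bleed. Nor does the quoted positive predictive value of 82.3% help, since it covers diagnosis codes overall and not this outcome.

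Three stronger readings are tempting and should be resisted.

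- *The double listing proves the error.* It does not. HAS-BLED bleeding history repeats the whole outcome list, acute codes included. The case rests on the ICD-10 meaning of I69 and on the I63/I69.3 contrast. That contrast is supportive only, because the HAS-BLED stroke item also includes I63 and G45.9.
- *The 6-month look-back misses all older bleeds.* It does not. A look-back finds codes recorded in the window, whatever the age of the bleed. The gap is patients with no code in that window. Channelling by coded history is likewise addressed in the propensity model.
- *A large part of the intracranial events will be false.* The 11–67% range reflects only the spread of the assumed inputs and says nothing about overall bleeding, which is the Phase II objective.

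**Conclusion.** The concern stands in a limited form. As written, the outcome can count an old intracranial bleed as a new one, and neither the baseline covariates nor the sensitivity analysis removes such events from the main analysis. The intracranial rows of SAP Table 18 are most exposed. The Phase I description of events before treatment change inherits the same definition.

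For overall major bleeding the effect is probably small: in the middle illustration about 1–8% of events, with an HR of 0.75 observed as about 0.77. These figures rest on assumed inputs and cannot be checked from the documents. The conclusion itself rests on the sequela meaning of I69 in ICD-10. The change should be made because it is cheap and specific; a serious distortion of the main result has not been shown.

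**What to change.** Delete I690, I691 and I692 from the intracranial outcome in SAP 8.4 and protocol Table 2. Keep them in HAS-BLED bleeding history and the stroke comorbidity. As a sensitivity analysis, repeat the comparison with the code list as it now stands, and report by treatment group how many intracranial outcomes rest on I69 codes alone. State which code list defines bleeding history in the existing 6-month sensitivity analysis.

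Requiring an acute code in the same admission would come to the same thing, because the acute code already qualifies.

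The cost is a code-list edit in two tables and one extra run. A true bleed coded only as I69.x would be lost, and the list would depart from the cited definition; the added sensitivity analysis shows how much either matters. The deletion does not deal with acute codes repeated as secondary diagnoses at later admissions.

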NOACs, or also known as direct oral anticoagulants (DOACs), are a relatively new generation of anticoagulants approved by the US FDA; dabigatran, rivaroxaban, apixaban, and edoxaban were approved in October 2010, July 2011, December 2012, and January 2015, respectively, for treatment indication of risk reduction of stroke and embolism in nonvalvular atrial fibrillation (NVAF) [6]. These NOACs have also been approved for prophylaxis and treatment of DVT and PE, which comprise VTE [7, 8]. Compared with VKAs, NOACs have fewer drug interactions, food interactions, and adverse effects and therefore, do not require frequent laboratory monitoring or dosage adjustments [4, 9]. Among NOACs, apixaban and rivaroxaban were approved as a single-drug approach for the treatment of VTE and do not require initial parenteral treatment with low molecular weight heparin (LMWH) or unfractionated heparin (UFH) [10, 11]. In actual real-world clinical practice, the two aforementioned NOACs are the most widely used and preferred treatments for VTE and preventing its recurrence [12-14]. Although NOACs demonstrated better safety profile than VKAs, concerns regarding their risk of adverse bleeding events remain due to their mechanism of action [15].

With both conventional and new anticoagulant therapies being used in real-world clinical practice, it is necessary to identify the utilization characteristics of individual anticoagulant treatments through the analysis of nationwide claims database. It is important to examine the treatment pattern and assess whether Korean patients are being treated appropriately based on the current treatment guidelines.

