8. RESEARCH METHODS

8.1. Study design

A retrospective, observational, nationwide population-based cohort study will be conducted to describe the treatment patterns of anticoagulation therapies prescribed to patients with VTE in South Korea, and assess the risk of major bleeding associated with apixaban and other NOACs use, as compared with warfarin, by using the Health Insurance Review and Assessment Service (HIRA) database from 1 Mar 2012 to 31 Dec 2019 (Figure 1).

Note: HIRA, Health Insurance and Review Assessment service; LMWH, low molecular weight heparin; NOAC, non-vitamin K antagonist; PAC, parenteral anticoagulants; VTE, venous thromboembolism; W, warfarin

[†]Record of active cancer is defined as first diagnosis of cancer with V code within the past 6 months of period prior to index date; or receiving anti-cancer treatment under cancer diagnosis with V code within the past 6-month period prior to index date.

[‡]Warfarin-based and NOAC-based include either PAC with warfarin/NOAC or warfarin/NOAC only

[figure not shown]
Figure 1. Study participants inclusion and exclusion criteria

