8.2. Study population

The study cohort will be defined as patients diagnosed with VTE between 1 Mar 2013 and 30 Jun 2019. The cohort entry will be defined as the date of incident VTE diagnosis. The index date will be defined as the date of first prescription for anticoagulants within 30 days after the index VTE event. The length of the exclusion assessment window will vary depending on the condition, from 12-months at minimum to anytime prior to index date. The following patients will be excluded: A record of VTE diagnosis within the 12-month period prior to the index VTE encounter, diagnosed with atrial fibrillation, atrial flutter, mechanical heart valve replacement or mitral stenosis anytime prior to index date, had a record of Inferior Vena Cava filter anytime prior to index date, received anticoagulatory therapy within the 12-month period prior to index VTE encounter to restrict to new users of anticoagulatory therapy, prescribed two different anticoagulants on the same index date to prevent exposure misclassification, had a record of pregnancy within the 9-month period prior to index date, and for the Phase II of the study only, had a record of active cancer within six months period prior to index date.

Baseline sociodemographic characteristics (e.g., age, sex) will be assessed on the index date, whereas clinical characteristics (comorbidities, previous use of medications, Charlson comorbidity index [CCI], HAS-BLED scores, initial presentation of VTE, number of outpatient visits) will be assessed in the 6-month period prior to the index date except when otherwise specified in section 8.4 *Variables* (Figure 2).

Within this study cohort, we will describe the treatment patterns of anticoagulants prescribed for VTE treatment throughout the period of follow-up, defined as the period from the index date to the end of the study period. Moreover, if feasible, we will also examine the risk of major bleeding overall and by site, associated with each NOAC use, as compared with warfarin.

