a. Baseline conditions included: Charlson comorbidity index, HAS-BLED scores, comorbidities (antiphospholipid syndrome, asthma, cancer, chronic obstructive pulmonary disease, chronic kidney disease, chronic liver disease, diabetes mellitus, fracture, heart failure, hyperlipidemia, hypertension, ischemic heart disease, myocardial infarction, stroke, trauma), previous use of medications (corticosteroids, nonsteroidal anti-inflammatory drugs, angiotensin-converting enzyme inhibitors, angiotensin II receptor blockers, antiplatelet agents, azole antifungal agents, β-blockers, calcium-channel blockers, selective serotonin reuptake inhibitors, proton pump inhibitors, diuretics, thiazides, vasodilators, estrogens, cyclooxygenase-2 inhibitors), initial presentation of VTE (DVT, PE, both DVT and PE), number of outpatient visits

b. Earliest of: outcome of interest (major bleeding event), treatment discontinuation, switch to another anticoagulant, in-hospital death, end of the study period (31 Dec 2019)

Note: Dx, diagnosis; NOAC, non-vitamin K antagonist oral anticoagulant; Rx, prescription; VTE, venous thromboembolism; PE, pulmonary embolism

Figure 2. Overall study schematic

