*Blood transfusion (Korean Procedure Codes: X1001, X1002, X2011, X2012, X2021, X2022, X2031, X2032, X2041, X2042, X2051, X2052, X2061, X2062, X2071, X2072, X2081, X2082, X2091, X2092, X2101, X2102, X2111, X2112, X2121, X2122, X2131, X2132, X2141, X2142, X3010) will also be used to define other site bleeding history.

- Initial presentation of VTE
 - DVT (I80.2, I80.3)

- PE (I26.0, I26.9)
- Both DVT and PE
- Comorbidities (ICD-10 diagnostic code) will be measured within the 6-month period prior to the index date.
 - Antiphospholipid syndrome (D68.6, I82.9): As diagnosis of antiphospholipid syndrome is usually made after VTE diagnosis with subsequent diagnostic procedures, its presence will be evaluated within the 6-month period after the index date.
 - Asthma (J45)
 - Cancer (C00-C97): History of cancer (non-active) will be evaluated within a lifetime prior to the index date.
 - Chronic obstructive pulmonary disease (COPD; J40-J44)
 - Chronic kidney disease (N18, N19)
 - Chronic liver disease (B18, B19, K70-K77)
 - Diabetes mellitus (E10-E14)
 - Fracture (S22, S32, S42, S52, S62, S72, S82, S92, T10, T12)
 - Heart failure (I50)
 - Hyperlipidemia (E78)
 - Hypertension (I10-I15)
 - Ischemic heart disease (I24, I25)
 - Myocardial infarction (I21)
 - Stroke (I60-I64, I69, G45)
 - Trauma (T79, T98, V01–V99, W11–W17, W50–W52, W64, X34–X39, Y01–Y04, Y30–Y32)
- Previous use of medications (WHO-ATC code) will be measured within the 6-month period prior to the index date.
 - Corticosteroids (H02)
 - Nonsteroidal anti-inflammatory drugs (NSAIDs; M01A)
 - Angiotensin-converting enzyme (ACE) inhibitors (C09A, C09B)

- Angiotensin II receptor blockers (ARBs; C09C, C09D)
- Antiplatelet agents (aspirin [N02BA01], aspirin/dipyridamole [B01AC30], abciximab [B01AC13], beraprost [B01AC19], cilostazol [B01AC23], clopidogrel [B01AC04], iloprost [B01AC11], indobufen [B01AC10], limaprost [C04AX], ozagrel [R03DX], prasugrel [B01AC22], sarpogrelate [B01AC], ticagrelor [B01AC24], ticlopidine [B01AC05], tirofiban [B01AC17], treprostinal [B01AC21], triflusal [B01AC18])
- Azole antifungal agents (fluconazole [J02AC01], itraconazole [J02AC02], voriconazole [J02AC03], posaconazole [J02AC04])
- β -blockers (C07)
- Calcium-channel blockers (C08)
- Selective serotonin reuptake inhibitors (SSRIs; N06AB)
- Proton pump inhibitors (PPIs; A02BC)
- Diuretics (C03)
- Thiazides (C03A)
- Vasodilators (C01D, C04A)
- Estrogens (G03C)
- Cyclooxygenase (COX)-2 inhibitors (M01AH)

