- In the NOAC-based group, all analyses will be repeated stratified by each individual NOAC class (e.g, apixaban, dabigatran, rivaroxaban, edoxaban) to

PFIZER CONFIDENTIAL

identify the difference in baseline characteristics and treatment patterns between each NOAC class.

- To identify potential reasons for treatment change, clinical events preceding the first treatment change (major bleeding, thromboembolism diagnosis, complications of VTE, major surgery, active cancer, a new diagnosis of CKD or AKI, a new diagnosis of liver disease or abnormal liver function) will be measured within 30 days prior to the first date of treatment change. Patients can contribute with multiple events.
- All analyses of treatment patterns will be presented stratified according to the index anticoagulant treatment, and not overall or per drug class.

Phase II of the study (comparative)

Propensity score analysis

- To balance and adjust for any potential differences in baseline sociodemographic and clinical characteristics between treatment groups, propensity score (PS) methods will be implemented.
 - A logistic regression model will be used to estimate the predicted probability (propensity) of initiating each NOAC compared with warfarin given baseline covariates mentioned above. By using the estimated PS, we will apply the PS based on the inverse probability of treatment weights (IPTW), where the treatment group of interest will be given a weight of 1/PS, and the comparator group will be given a weight of 1/(1-PS) [4, 5]. The most extreme 1% of PS values (IPTW with trimming) will be excluded to improve comparability between exposure groups.

Main Analysis

- Sociodemographic and clinical characteristics will be summarized with means (STD) or median (IQR) for continuous variables and with count (proportions) for categorical variables for the two treatment comparisons of: apixaban vs warfarin, rivaroxaban vs warfarin, edoxaban vs warfarin and dabigatran vs warfarin (and NOAC vs NOAC, if scientifically feasible).
 - Differences in baseline covariates between users of different OACs will be assessed using the SD where the absolute SD <0.1 will be considered as well balanced.
- The incidence rate of major bleeding overall and by site will be presented as the total number of events per 1,000 person-years, with its 95% CIs estimated using the Poisson distribution.

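### The Phase II propensity score has no measure of index-PE severity or reperfusion treatment, so any imbalance between drugs would remain in the primary hazard ratios; its direction and size cannot be told from the documents.

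*SAP*

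**What the plan says.** The confounder list in SAP 8.4 gives the initial presentation three levels, with PE defined as "PE (I26.0, I26.9". Protocol 9.3 has the same coding. The Figure 2 note in SAP 8.2 repeats it as "initial presentation of VTE (DVT, PE, both DVT and PE". The VTE-type subgroup in SAP 10 also pools the two PE codes.

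For drugs, SAP 8.4 states: "Previous use of medications (WHO-ATC code) will be measured within the 6-month period prior to the index date". The list that follows contains no thrombolytic. No reperfusion procedure appears among the covariates, exclusions, subgroups or sensitivity analyses in either document.

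The propensity model in SAP 10 estimates the probability of "initiating each NOAC compared with warfarin given baseline covariates mentioned above", so only listed items can enter.

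Time zero is set in SAP 8.2: "The index date will be defined as the date of first prescription for anticoagulants within 30 days after the index VTE event". That first anticoagulant may be heparin, because the Figure 1 footnote in SAP 8.1 says: "Warfarin-based and NOAC-based include either PAC with warfarin/NOAC or warfarin/NOAC only". For the outcome, SAP 8.4 says "Patients will be followed up from the index date to the occurrence of an outcome", and dates the event at the earliest bleeding diagnosis after the index date. There is no lag.

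**The concern.** Two patients with PE can differ greatly in early bleeding risk, depending on how severe the embolism was and whether it was lysed or removed by catheter or surgery. If severity also influences the choice of oral drug, it confounds the comparison of each NOAC with warfarin. Protocol 7 gives one reason why choice might depend on it: "apixaban and rivaroxaban were approved as a single-drug approach for the treatment of VTE and do not require initial parenteral treatment".

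The propensity score can balance DVT against PE but nothing within PE. The other planned approaches (5% and 10% trimming, the score as a covariate, deciles, standardized mortality ratio weights) all draw on the same covariates, so agreement among them would not show that severity is balanced. At stake is residual confounding in the primary hazard ratios for major bleeding. Part of it is avoidable, because the two PE codes are already in the data.

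**Working it through.** **What the score can see.** CCI, HAS-BLED, comorbidities and medications describe the months before index. None describes the index PE. The 6-month medication window would already pick up thrombolysis given between diagnosis and the day before index, but no such drug is listed. Diagnosis setting is a subgroup and is not a listed confounder. Table 1 has an index-VTE row; the balance Tables 13–16 have none, so even DVT/PE balance would not be shown.

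**Yardsticks from the plan.** No stated figure depends on this point, so the targeted hazard ratios serve as the scale. They reproduce with the Schoenfeld formula, N = (1.960 + 0.842)² / [p(1 − p)(ln HR)²] / event probability. For rivaroxaban at 1.19: 7.849 / (0.691 × 0.309 × 0.174²) ≈ 1,215 events, and 1,215 / 0.081 ≈ 15,000, against the stated 14,967. On the log scale the smallest targets are rivaroxaban 1.19 (0.174), edoxaban 0.81 (0.211), rivaroxaban 0.77 (0.261) and apixaban 0.75 (0.288).

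**Illustration of size.** Every input here is an assumption; the documents give none of them.
- f = 0.45, share of patients with PE (equal in both groups after weighting)
- s = 0.03, 0.05 or 0.10, share of PE that is severe or lysed
- a = 0.4, NOAC share among the other PE patients
- OR = odds ratio for receiving a NOAC, severe versus other PE
- R = 3 or 5, bleeding rate ratio for severe PE

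Formulas:
- p₁ = OR·o / (1 + OR·o), with o = a/(1 − a)
- e = (1 − s)a + s·p₁
- q_N = f·s·p₁/e and q_W = f·s(1 − p₁)/(1 − e)
- apparent HR when the truth is 1.00: B = [1 + q_N(R − 1)] / [1 + q_W(R − 1)]

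Extreme case (s = 0.10, OR = 0.33, R = 5): p₁ = 0.22/1.22 = 0.180; e = 0.378; q_N = 0.0215; q_W = 0.0593; B = 1.086/1.237 = 0.878.

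Middle case (s = 0.05, OR = 0.5, R = 3): p₁ = 0.25; e = 0.3925; q_N = 0.0143; q_W = 0.0278; B = 1.0287/1.0556 = 0.975.

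| s | R | OR 0.33 | OR 0.5 | OR 2 |
|---|---|---|---|---|
| 3% | 3 | 0.977 | 0.984 | 1.018 |
| 3% | 5 | 0.955 | 0.969 | 1.036 |
| 5% | 3 | 0.963 | 0.975 | 1.029 |
| 5% | 5 | 0.929 | 0.952 | 1.057 |
| 10% | 3 | 0.932 | 0.954 | 1.054 |
| 10% | 5 | 0.878 | 0.916 | 1.101 |

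Of the twelve cells with OR below 1, nine are 0.93 or higher and one is near 0.88. Equal odds (OR = 1) give exactly 1.00.

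The NOAC share matters somewhat. At edoxaban's 31.0% the extreme cell stays at 0.88. At rivaroxaban's 69.1% it is 0.85 (q_N = 0.0288, q_W = 0.0771, B = 1.115/1.309).

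Relative to ln 1.19 = 0.174, the table's extreme cell is 0.130/0.174 ≈ 75%, the middle cell 0.026/0.174 ≈ 15%, and the largest reversed cell 0.096/0.174 ≈ 55%.

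**Would a modest shift show as significant?** Projected N times event probability gives 89,124 × 0.081 ≈ 7,219 events for rivaroxaban and 49,224 × 0.0119 ≈ 586 for apixaban. A pure-bias shift from 1.00 to 0.95 has z = √[events·p(1 − p)]·|ln 0.95|. For rivaroxaban this is 39.3 × 0.0513 = 2.01, so p < 0.05 about 52% of the time; for apixaban the figure is about 9%. This ignores the extra variance from weighting.

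**The case against.** The strongest reply is that no bias has been shown. That is correct: without prevalence of severe or lysed PE by drug, the sign is unknown and the bias may be zero. Several stronger readings are tempting and are not supported.

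- A reader might infer that the hazard ratios will be tilted in favour of the NOACs. The heparin-free start that Protocol 7 describes concerns apixaban and rivaroxaban only, and a parenteral start does not separate warfarin from NOACs here, since both groups may include bridged patients. Reversed channelling gives values above 1.
- A reader might infer that all early bleeding is charged to the oral drug. Only diagnoses after the index date count, patients who never start an oral drug stay in the PAC-only group outside Phase II, and patients given two anticoagulants on the index date are excluded.
- A reader might take 0.88 as the expected size, or judge it against edoxaban 0.81 as the smallest target. It is one corner of an assumed grid, and rivaroxaban 1.19 is the smaller target. The grid also applies a constant rate ratio; if the excess is confined to the first days, an average of 3 to 5 over all follow-up would need a still higher early ratio.

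The plan also has partial checks. The DVT-without-PE subgroup is free of PE severity, and the outpatient subgroup should contain little of it. Protocol 9.9 acknowledges residual confounding and plans an E-value, but words it for apixaban only, and the SAP sensitivity list omits it. These could hint at a problem. None adjusts for severity within PE or shows whether it is balanced.

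**Conclusion.** The gap is real: the two PE codes are pooled, reperfusion is absent from every analysis, and no planned variation of the propensity score can compensate. The consequence is conditional: confounding by severity remains if severe or lysed PE is unevenly distributed between a NOAC and warfarin after weighting. Under the assumed inputs a null effect would appear as 0.88 to 0.98, mostly 0.93 or higher, or as 1.02 to 1.10 with the odds ratio reversed to 2. That ranges from minor to a substantial part of the smallest targeted effect. The documents support neither a direction nor a point estimate.

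Reading I26.0 and I26.9 as PE with and without acute cor pulmonale uses the standard ICD-10 labels, which the documents do not spell out. The reperfusion gap does not depend on that reading. This is a worthwhile, inexpensive improvement to the analysis and not proof that the primary results would be wrong.

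**What to change.** In SAP 8.4 and Protocol 9.3:

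1. Enter the initial presentation as DVT only, PE with I26.0, and PE with I26.9 only, each PE level with or without DVT.
2. Add a binary covariate for a thrombolytic drug, or catheter or surgical thrombectomy, from the VTE diagnosis up to and including the index date, with its code list.
3. Put both in each propensity model, and add rows for index VTE type and the new covariate to Tables 13–16.
4. Add one row to Table 20 that excludes patients with thrombolysis or thrombectomy by the index date.

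The cost is one code list, a few propensity-model terms, the balance rows and one sensitivity row; the sample size is unaffected. Adjustment will be partial: I26.0 may be under-coded, and reperfusion given after the day heparin starts is missed. Extending the window past index to catch it would condition on post-index events, so the window should stay closed at the index date and the limitation be stated.
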